**Table 5: Cross-Titration Scheme from End of 14-Week Treatment Period in Part A to Start of Part B**

Study Part/ Visit	Visit Type	Study Day	GWP42003-P 10 mg/kg/day			GWP42003-P 15 mg/kg/day			GWP42003-P 20 mg/kg/day			Placebo		
			Blinded (mg/kg/day)	OL (mg/kg/day)	Total Dose (mg/kg/day)	Blinded (mg/kg/day)	OL (mg/kg/day)	Total Dose (mg/kg/day)	Blinded (mg/kg/day)	OL (mg/kg/day)	Total Dose (mg/kg/day)	Blinded (mg/kg/day)	OL (mg/kg/day)	Total Dose (mg/kg/day)
Part A Visit 9	C	99	10	0	10	15	0	15	20	0	20	0	0	0
Part B Visit 1	C	1-7	5	5	10	10	5	15	15	5	20	0	5	5
Part B Visit 2	P	8-14	0	10	10	5	10	15	10	10	20	0	10	10
Part B Visit 3	P	15-21	-	10 or 15	10 or 15	0	10 or 15	10 or 15	5	10 or 15	15 or 20	0	10 or 15	10 or 15
Part B Visit 4	P	22-28	-	10, 15, or 20	10, 15, or 20	-	10, 15, or 20	10, 15, or 20	0	10, 15, or 20	10, 15, or 20	0	10, 15, or 20	10, 15, or 20

Abbreviations: C = clinic; OL = open-label; P = phone.

## **6.6. Continued Access to Study Intervention After the End of the Study**

There is no plan to provide continued access to IMP after the end of the study.

## **6.7. Treatment of Overdose**

For this study, any dose of IMP > 20 mg/kg within a 24-hour period may be considered an overdose, based on investigator's or sponsor's discretion.

In the event of overdose, the participant should be treated symptomatically (supportive management) according to local guidelines and in line with the current approved version of the IB.

In the event of an overdose, the investigator should:

- Closely monitor the participant for any AE/SAE including any laboratory abnormalities as clinically indicated.
- Contact the medical monitor as soon as possible.
- Evaluate the participant to determine, in consultation with the medical monitor (when possible), whether the IMP should be interrupted or whether the dose should be reduced.
- Document the quantity of the excess dose as well as the duration of the overdose.
- Instructions on missed doses and/vomiting will be included in a separate pharmacy manual.

## **6.8. Concomitant Therapy**

Caution should always be exercised when allowing administration of concomitant therapies according to the individual profile and clinical risk-benefit assessment. Key restrictions on concomitant therapies that apply to the period before screening and during the study are briefly summarized below. Additional restrictions and details are described further in [Section 5.1](#) and [Section 5.2](#).

- Current treatment with 1 or more ASMs or a vagal nerve stimulator are allowed; change in anticonvulsant therapies (including ASMs or vagal nerve stimulator settings) are not permitted within 28 days of starting the baseline period (Part A Visit 2), and no changes to these therapies should be planned for the duration of the study.
- Previous treatment with felbamate within 12 months prior to screening (Part A Visit 1) is prohibited. However, participants who are stable on felbamate for  $\geq 12$  months are eligible.
- Current therapy with ketogenic diet/epilepsy dietary therapy is allowed as long as dietary therapy has been stable ( $\geq 28$  days prior to starting the baseline period [Part A Visit 2]) and no changes to therapy are planned for the duration of the study.

- Current therapy with Epidiolex/Epidyolex or recent treatment with Epidiolex/Epidyolex within 28 days prior to screening (Part A Visit 1) is not permitted.
- Previous treatment with Epidiolex/Epidyolex that resulted in a lack of efficacy and/or poor tolerability is prohibited. However, participants who discontinued treatment for reasons other than safety, tolerability, or lack of efficacy and previously received Epidiolex/Epidyolex  $\geq 28$  days prior to screening (Part A Visit 1) may be eligible for the study after consultation with the medical monitor and/or sponsor representative.
- Current use or recent use (within 28 days prior to screening [Part A Visit 1]) of recreational or medicinal cannabis, cannabinoid-based medications, products, or supplements (botanical or synthetic) is prohibited.
- If the study participant is being breastfed, current use or recent use (within 28 days prior to screening [Part A Visit 1]) by the mother of recreational or medicinal cannabis, cannabinoid-based medications, products, or supplements (botanical or synthetic) is prohibited.

Any vaccination related to SARS-CoV-2 (COVID-19) that was received within the last 12 months prior to screening (Part A Visit 1) or during the study should be recorded as concomitant medication. The information recorded should include the vaccine manufacturer and the dates of administration; differing start and end dates if more than 1 dose is received.

Any medication or vaccine (including over-the-counter or prescription medicines, recreational drugs, vitamins, and/or herbal supplements) that the participant is receiving within 3 months of screening (Part A Visit 1) or receives during the study must be recorded along with:

- Reason for use.
- Dates of administration including start and end dates.
- Dosage information including dose and frequency.

Additionally, all ASMs, antiepileptic therapies, and rescue medications taken during the participant's life (previous and/or current use) will be recorded in the eCRF and reviewed at each subsequent visit.

The medical monitor should be contacted if there are any questions regarding concomitant or prior therapy.

It is possible that GWP42003-P oral solution may modify the metabolism of other drugs (including other ASMs) administered concurrently and there remains the possibility of pharmacological interactions between GWP42003-P oral solution and other concurrently administered drugs. **Detailed information on potential drug interactions can be found in the current approved GWP42003-P IB in the “CBD Dose Adjustment” section.**

Concomitant ASM dose reductions are permitted on clinical grounds (eg, due to AEs or transaminase elevations not meeting withdrawal criteria specified in [Section 7.1](#)) following discussion with the medical monitor.

## 7. DISCONTINUATION OF STUDY INTERVENTION AND PARTICIPANT DISCONTINUATION/WITHDRAWAL

Participants have the right to withdraw from the IMP and/or other protocol-required therapies, protocol procedures, or the study as a whole at any time and for any reason without prejudice to their future medical care by the physician or at the institution.

The investigator can withdraw a participant(s) from IMP, and/or other protocol-required therapies, protocol procedures, or the study as a whole at any time prior to study completion for the reasons listed in [Section 7.1](#) and [Section 7.2](#).

### 7.1. Discontinuation of Study Intervention

Reasons for removal from IMP include any of the following:

- Participants may decline to continue receiving IMP or other protocol-required therapies or procedures at any time during the study.
  - Participants who choose to discontinue IMP or other protocol-required therapies or procedures should not be automatically removed from the study. Whenever safe and feasible, and in agreement with the sponsor, the participants should remain in the respective part of the study to ensure safety surveillance and collection of outcome data. Specifically, participants who discontinue IMP prematurely in Part A of the study will not be enrolled in Part B.
  - The investigator is to discuss with the participant the appropriate processes for discontinuation from IMP or other protocol-required therapies. The investigator must discuss with the participant the possibilities for continuation of activities described in the SoA ([Table 1](#) and [Table 2](#)) and must document this decision in the eCRF.
- Decision by investigator.
- Decision by sponsor.
- Withdrawal by participant/caregiver/legal representative.
- Lack of efficacy.
- Change in compliance with any inclusion/exclusion criterion that is clinically relevant and affects participant safety, as determined by the investigator (or designee).
- Protocol deviation that is considered to potentially compromise the safety of the participant.
- Noncompliance with IMP.
- Noncompliance with study assessments.
- Pregnancy.
- Liver Chemistry - Discontinuation of IMP for abnormal liver tests is required by the investigator when a participant meets one of the following conditions outlined or in

the presence of abnormal liver chemistries not meeting protocol-specified stopping rules if the investigator believes that it is in best interest of the participant.

- Serum ALT or AST  $> 3 \times \text{ULN}$  with the presence of fatigue, nausea, vomiting, right upper quadrant pain or tenderness, fever, rash, and/or eosinophilia ( $> 5\%$ ).
- ALT or AST  $> 8 \times \text{ULN}$ .
- ALT or AST  $> 5 \times \text{ULN}$  for  $> 2$  weeks.
- ALT or AST  $> 3 \times \text{ULN}$  **and** (TBL  $> 2 \times \text{ULN}$  **or** INR  $> 1.5$ ).
- Note: Refer to [Section 10.6](#) (Appendix 6) for information on follow up for clinically significant liver results.
- Any evidence of drug abuse or diversion.
- Suicidal behavior or Serious suicidal ideation during the treatment period, defined as Item 4 or Item 5 on the C-SSRS.
- An AE (including clinically significant laboratory result) which, in the opinion of the investigator, would compromise the continued safe administration of IMP to the participant in the study.

## 7.2. Participant Withdrawal from the Study

A participant may withdraw from the study at any time at his/her own request or may be withdrawn at any time at the discretion of the investigator or sponsor for safety, behavioral, or compliance reasons.

- The participant will be permanently discontinued both from the IMP and from the study at that time.
- If a participant is withdrawn from the study, the study monitor will be informed immediately. If there is a medical reason for withdrawal, the participant will be followed up by the investigator until satisfactory health has returned.
- All efforts must be made to complete and report the observations as thoroughly as possible up to the date of withdrawal.
- Participants withdrawing due to an AE should be followed up according to [Section 10.4.4](#). All information should be reported on the applicable eCRF pages (refer to [Section 8](#)). A safety follow-up visit should take place  $\pm 7$  days after last dose of IMP (refer to [Table 1](#) and [Table 2](#)). If withdrawing participants decline to give a reason for withdrawal of consent, the investigator must respect the participant's wishes.
- If the participant withdraws consent for disclosure of future information, the sponsor may retain and continue to use any data collected before such a withdrawal of consent.
- If a participant withdraws from the study, he/she may request destruction of any samples taken and not tested, and the investigator must document this in the site study records.

Reasons for removal of a participant from the study are:

- Decision by investigator.
- Decision by sponsor.
- Lack of efficacy.
- AE.
- Withdrawal by participant/caregiver/legal representative.
- Death.
- Lost to follow up.

### **7.3. Lost to Follow up**

A participant will be considered lost to follow-up if he or she fails to return for scheduled visits and/or is unable to be contacted by the study site.

The following actions must be taken if a participant fails to return to the clinic for a required study visit:

- The site must attempt to contact the participant and reschedule the missed visit as soon as possible and counsel the participant on the importance of maintaining the assigned visit schedule and ascertain whether or not the participant wishes to and/or should continue in the study.
- Before a participant is deemed lost to follow up, the investigator or designee must make every effort to regain contact with the participant (where possible, 3 telephone calls and, if necessary, a certified letter to the participant's last known mailing address or local equivalent methods). These contact attempts should be documented in the participant's medical record.
- Should the participant continue to be unreachable, he/she will be considered to have withdrawn from the study.
- Site personnel, or an independent third party, will attempt to collect the vital status of the participant within legal and ethical boundaries for all participants randomized, including those who did not get the IMP. Public sources may be searched for vital status information. If vital status is determined as deceased, this will be documented, and the participant will not be considered lost to follow up. Sponsor personnel will not be involved in any attempts to collect vital status information.

Discontinuation of specific sites or of the study as a whole are handled as part of [Section 10.2.9](#).

## 8. STUDY ASSESSMENTS

Study procedures and their timing are summarized in the SoA ([Section 1.3](#)).

- Immediate safety concerns should be discussed with the sponsor immediately upon occurrence or awareness to determine if the participant should continue or discontinue IMP.
- Adherence to the study design requirements, including those specified in the SoA ([Section 1.3](#)), is essential and required for study conduct.
- All screening evaluations must be completed in the source records and reviewed to confirm that potential participants meet all eligibility criteria. The investigator will maintain a screening log to record details of all participants screened and confirmation of eligibility or record reasons for screening failure, in the eCRF as applicable.
- Safety/Laboratory/analyte results that could unblind the study will not be reported to investigational sites or other blinded personnel until the study has been unblinded.

### 8.1. General Assessments

#### 8.1.1. Demographics

At screening (Part A Visit 1), the following information will be obtained for each participant: age, sex, race, ethnic origin (if allowed per local regulation or if otherwise supported by the scientific rationale).

#### 8.1.2. Medical History

Full medical history, including perinatal history, and EEG report (historical EEG report can be used to determine eligibility at screening if performed within the past 12 months prior to screening [Part A Visit 1]) will be obtained during screening and is defined as any condition or disease that meets any of the following criteria:

- May affect the condition under study.
- Including complete seizure history, developmental history, lifetime history of epilepsy, history of *status epilepticus*, and any hospitalizations.
- Is ongoing on entry into the study.
- Has occurred within 1 year prior to screening (Part A Visit 1).
- Suspected or confirmed COVID-19 infection (or other significant communicable diseases) within 1 year prior to screening (Part A Visit 1).
- Information required for TESC confirmation of EMAS diagnosis and/or seizure classification, including but not limited to lifetime imaging history, EEG history, genetic testing history, etc.
- Gastrostomy or nasogastric tube placement.
- Prior cannabis use.

- Historical vaccinations.

### **8.1.3. Interactive Response Technology**

The IRT (RTSM) will be used to assign participants to treatment groups, manage IMP supply, and to provide treatment allocation information in the event of participant unblinding. The RTSM will be integrated with Rave electronic data capture.

A member of the study team must register in the eCRF at each clinic visit in order to:

- Obtain a participant's number at screening (Part A Visit 1).
- Randomize a participant (Part A Visit 3).
- Obtain dispensing information on day of visit (Part A Visits 3, 7, 8, and 9; Part B Visits 1, 5, 6, 7, 8, and 10). If required for home health visits, dispensing information may be obtained 1 day prior to visit.
- Provide completion/taper/premature termination information (after Part A Visit 3).

Training will be given to all sites prior to the start of the study.

### **8.1.4. Participant eDiary**

An eDiary will be completed throughout the study, until the end of the taper period (Part A Visit 10; Part B Visit 11) or early withdrawal visit (Part A Visit 9; Part B Visit 10). If the participant is provided with a site-provisioned eDiary, the device must be returned to the site at the last clinic visit. A back-up plan to record eDiary data will be in place in case of any device failure.

Caregivers will record the following information in the eDiary:

- AEs, concomitant medications, rescue medication, and seizures (including type, number, and days with *status epilepticus*) beginning at screening (Part A Visit 1).
- Food eDiary module beginning approximately 24 hours prior to randomization (Part A Visit 3) and 24 hours prior to Part A Visit 9 (or End of Treatment Visit if the participant discontinues treatment prior to Part A Visit 9) – details of each meal consumed by the participant within approximately 24 hours prior to **PK collection**, including the date, time, and meal type:
  - High fat meal (dairy or meat)
  - Standard meal (fruit or vegetable)

Other (if not fitting into one of the categories above)

- IMP dosing eDiary module beginning at randomization (Part A Visit 3) – IMP usage, including dose time, volume administered, and consistency of IMP dosing with respect to mealtimes.

Caregivers will be instructed to immediately contact the investigator by phone to discuss any changes in their child's health (possible AEs), changes in concomitant medications, including ASMs, use of rescue medication, and days with *status epilepticus* or potential new seizure types.

All eDiary entries will be reviewed and discussed with the caregiver for verification during participant phone or clinic visits. This review will be documented in the source and eCRF.

- For the AE, concomitant medication, and rescue medication eDiaries, details on AEs, changes in concomitant medications, including ASMs and use of rescue medication will be recorded within the source documents and eCRF.
- For the seizure eDiary, any days with *status epilepticus* will be recorded in the source and reported as an SAE; any potential new seizure types will be recorded in the source and reported to TESC for adjudication. New seizure types may be added to the eCRF as expected seizure types following TESC approval.

#### **8.1.5. Confirmation of EMAS Diagnosis and Seizure Classification**

To ensure accurate diagnosis of EMAS according to ILAE criteria ([International League Against Epilepsy 2012](#)) ([Trinka 2015](#)), investigators will collect lifetime developmental and lifetime seizure history during screening (Part A Visit 1) using the SIF/DRF and eDiary Seizure Classification Report.

Caregivers will begin reporting seizures to the seizure eDiary immediately following screening (Part A Visit 1) and will continue reporting seizures to the seizure eDiary for the remainder of the study.

The investigator will submit the completed SIF/DRF and eDiary Seizure Classification Report directly to TESC within 24 hours (1 business day) of screening (Part A Visit 1), where possible. TESC may ask the investigator for additional information to assist in their decision. The Epilepsy Study Consortium decision will be made within 14 days of receipt of all required information and written approval of the SIF/DRF and eDiary Seizure Classification Report must be received by the investigator before the baseline (Part A Visit 2) can occur.

At baseline (Part A Visit 2), the investigator will contact the caregiver by phone for seizure classification training (eg, to review TESC-approved eDiary Seizure Classification Report and train the caregiver to identify, count and report the participant's TESC-approved seizures to the seizure eDiary). Only seizures reported from the start of baseline (Part A Visit 2) will be used for the participant's baseline seizure count.

**Only seizures that are recognizable and countable will be reported by caregivers for this study.**  
The following ILAE seizure subtypes may be collected in the eDiary:

- Primary endpoint EMAS-associated seizures:
  - Myoclonic-ataxic
  - Atonic
  - Tonic
  - Clonic
  - Tonic-clonic
- Secondary endpoint seizures:
  - Myoclonic seizures

- Total Seizures (primary endpoint seizures and other seizures)
  - [REDACTED]
  - [REDACTED]
  - [REDACTED]
  - [REDACTED]
  - [REDACTED]
- *Status epilepticus* (any seizure lasting 30 minutes or longer)
  - Convulsive *status epilepticus*
  - Non-convulsive *status epilepticus*

### **8.1.6. Investigational Medicinal Product Accountability**

Records of IMP accountability will be maintained according to [Section 6.2](#) and [Section 6.4](#).

## **8.2. Efficacy Assessments**

Planned time points for all efficacy assessments are provided in the SoA ([Section 1.3](#)).

### **8.2.1. Questionnaires and Assessments Completed at Scheduled Visits**

Non-investigator/physician-facing questionnaires should be completed by the main caregiver. The questionnaires will be captured using an electronic system. The same person should complete the questionnaires/assessments throughout the study to maintain consistency. If the main caregiver is not available at the appropriate visit, then this information can be captured over the telephone, ideally on the day of the visit or otherwise within  $\pm$  7 days. Because participants in this study are expected to be experiencing varying degrees of cognitive impairment or delay related to their seizure history, only completion of caregiver-facing questionnaires are expected for this study.

Investigator/physician-facing questionnaires should be completed by the appropriate rater and data will be recorded in an electronic system, ideally on the day of the visit or otherwise within  $\pm$  7 days. The same person should complete the questionnaires/assessments throughout the study to maintain consistency.

The participant's age at Part A Visit 1 will be used to determine which questionnaires should be completed for the duration of the trial. Questionnaires should only be administered to study participants who satisfy minimum age requirements at screening (Part A Visit 1). Questionnaires completed during screening (Part A Visit 1) will be considered as baseline.

Questionnaires should be completed prior to any invasive procedures (eg, blood draws, ECG, EEG, etc.) that may affect the caregiver's responses to the questionnaires.

Questionnaires will only be administered if a translation is available in the caregiver's native language.

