**Table 1: Schedule of Activities: Part A**

Study Period	Screening	Baseline Period	14-Week Dose-Optimization Treatment Period						EOT or E/W	Taper Period	Safety FU	Notes
Visit Number	1	2	3	4	5	6	7	8	9	10	11	
Week	-	-	0	1	2	3	4	8	14	16	20	
Day	-49 to -35	-28	1	8	15	22	29	57	99	110	138	
Visit Window (days)	-	-	+3	±3	±3	±3	±3	±7	±7	+3	±7	
Visit Type	Clinic	Phone	Clinic	Phone	Phone	Phone	Clinic	Clinic*	Clinic	Clinic	Phone	
Pharmacokinetics												
PK blood			X						X			Section 8.5 and Section 8.1.4
Safety and Tolerability												
CEQ-P	X											
Tanner Staging	X								X			
Menstruation question			X						X			Female participants only
CGIC	X								X			Memory aid only at Part A Visit 1
PGIC	X								X			Memory aid only at Part A Visit 1
Biochemistry & Coagulation	X		X				X	X	X			Section 8.3
Hematology	X		X				X		X			Section 8.3

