**Table 2: Schedule of Activities: Part B**

Study Period	Dose Escalation		Dose Optimization Treatment Period (Flexible Titration)								EOT or E/W	Taper Period	Safety FU	Notes
Visit Number	1		2	3	4	5	6	7	8	9	10	11	12	
Week	0	1	2	3	4	8	14	24	36	48	50	54		
Day	1	8	15	22	29	57	99	169	253	337	348	376		
Visit Window (days)	-	$\pm 3$	$\pm 3$	$\pm 3$	$\pm 3$	$\pm 7$	$\pm 7$	$\pm 7$	$\pm 7$	$\pm 7$	$\pm 3$	$\pm 7$		
Visit Type	Clinic	Phone	Phone	Phone	Clinic	Clinic*	Clinic	Clinic*	Phone	Clinic	Clinic	Phone		
PGIC							X	X		X				
Biochemistry & Coagulation	X				X	X	X	X		X				Section 8.3
Hematology	X				X		X			X				Section 8.3
Urinalysis	X				X		X			X				Section 8.3
ECG	X				X		X			X				Section 8.3.3
Vital signs	X				X	X	X	X		X	X			Section 8.3.2
C-SSRS	X	X	X	X	X	X	X	X	X	X	X	X		
AE review	<=====>													
Prior/concomitant medication review	<=====>													

Abbreviations: AE = adverse event; BID = twice daily;

C-SSRS = Columbia Suicide-Severity Rating Scale; CGIC = Caregiver Global Impression of Change;

E/W = early withdrawal; ECG = 12-lead electrocardiogram; EOT = end of treatment; FU = follow-up; IMP = investigational medicinal product;

PGIC = Physician Global Impression of Change.

Note: \*Clinic or home nurse. For visits carried out remotely, home nurse assessments include: collection/dispensation of IMP, blood samples, height, length, head circumference, and vital signs.

Note: Part B Visit 1 is the same as Part A Visit 9. Data collected at Part A Visit 9, will be considered as Part B Visit 1 data. Procedures completed at Part A Visit 9 should not be repeated at Part B Visit 1.

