Participants will complete weekly scheduled phone visits at Day 8 (Visit 4), Day 15 (Visit 5), and Day 22 (Visit 6) and complete an in-clinic visit at Day 29 (Visit 7) and an in-clinic or home visit for review of symptoms and safety laboratory tests and to return/dispense IMP at Day 57 (Visit 8). Participants will then return to the study site for an end of treatment visit (Day 99 [Visit 9]). If a participant withdraws from the study prematurely (ie, before the end of treatment visit), an early withdrawal visit will be conducted, and a safety follow-up phone call will occur 4 weeks after their last dose of IMP. If a participant discontinues IMP prematurely, they should be encouraged to complete the end of treatment visit and the taper period and remain in the study.

Participants not continuing to Part B will return to the study site again at the end of the 10-day taper period (Day 110 [Visit 10]) and will complete a phone safety visit at the end of the follow-up period (Day 138 [Visit 11]).

Part B will be available to participants who complete Part A of the study and continue to meet all eligibility criteria and to participants for whom the investigator feels continued treatment in Part B represents a favorable risk-benefit assessment. Rollover into Part B should occur on the same day as Part A Day 99 (Visit 9).

Unscheduled phone visits can occur at any time throughout Part A, as needed.

AE, concomitant medication, and rescue medication eDiaries will be completed each day during the screening period, baseline observation period, treatment period, and taper period beginning at screening (Visit 1).

Seizure eDiaries will be completed each day during the screening period, baseline observation period, and treatment period beginning at screening (Visit 1).

IMP dosing eDiaries will be completed each day during the titration, treatment, and taper periods beginning at randomization (Visit 3).

Food eDiaries will be completed for approximately 24 hours prior to each visit where PK blood samples will be collected beginning approximately 24 hours prior to randomization (Visit 3).

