### **8.5. Pharmacokinetic Assessments**

PK assessments will only be performed for Part A of the study. Plasma samples will be collected from all participants for measurement of plasma concentrations of CBD and its major metabolites as specified in the SoA ([Section 1.3](#)) as follows:

- Pre-dose (within 60 minutes prior to the morning dose of IMP).

- Post-dose (3 hours [ $\pm 1$  hour]) following morning dose of IMP).

Instructions for the collection and handling of biological samples will be provided by the sponsor. The actual date and time (24-hour clock time) of each sample will be recorded.

Samples will be used to evaluate the PK of CBD and its major metabolites.

IMP concentration information that may unblind the study will not be reported to investigative sites or blinded personnel until the study has been unblinded.

The maximum amount of blood taken for PK analysis will be approximately 4 mL.

Caregivers will record the date, time, and meal type (eg, high fat meal [dairy or meat], standard meal [fruit or vegetable] or other [if not fitting into one of the categories above]) for all meals consumed by the participant within 24 hours prior to PK collection.

Analysis of all PK samples will be conducted at a central bioanalytical laboratory and additional details are provided in the laboratory manual.

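### The only post-baseline Part A CGIC may be collected by telephone up to 7 days after Visit 9, when Part B or taper dosing has already begun

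*Combined protocol and SAP*

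**What the plan says.** Section 8.2.1 sets the collection rule for caregiver questionnaires. Its condition is "If the main caregiver is not available at the appropriate visit". Where that condition is met, a telephone rating is allowed: "then this information can be captured over the telephone, ideally on the day of the visit or otherwise within" a margin of ±7 days. The rule covers every visit and does not single out Part A Visit 9.

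The other relevant provisions are these:

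- **CGIC schedule.** Table 1 marks CGIC at Part A Visits 1 and 9 only, with the note "Memory aid only at Part A Visit 1". Visit 9 (Day 99) is therefore the single Part A rating of change.
- **Start of Part B.** The Table 2 note says "Part B Visit 1 is the same as Part A Visit 9", and section 4.1 says "Rollover into Part B should occur on the same day as Part A Day 99 (Visit 9").
- **Dosing after Visit 9.** Table 5 gives former placebo participants 5 mg/kg/day of open-label drug on Part B Days 1-7 and 10 mg/kg/day on Days 8-14. Table 1 has participants who do not roll over reducing the dose by 10% per day for 10 days.
- **Order within the visit.** Section 8.2.1 adds "Questionnaires should be completed prior to any invasive procedures". Section 8.5 times the first PK sample as "Pre-dose (within 60 minutes prior to the morning dose of IMP").
- **Use of the rating.** CGIC at Week 14 is the second key secondary endpoint. Section 9.4.3.1 analyses it with a Bayesian hierarchical ordinal logistic model.

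**The concern.** At most visits a week's latitude for a telephone rating does little harm. Visit 9 differs because the randomized comparison ends there and treatment changes the same day. A rating given after the visit can reflect up to about a week of active drug in a former placebo participant, or a partly withdrawn dose in an active-arm participant who is tapering. Either would tend to pull the arms together. No second Part A rating exists to replace a late one.

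What is at stake is a slight loss of sensitivity on a key secondary endpoint, not a false positive. Rollover does not reveal the Part A arm, since the Part B transition is blinded.

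No equivalent claim is made for PGIC. For physician questionnaires section 8.2.1 says "data will be recorded in an electronic system, ideally on the day of the visit or otherwise within" ±7 days, which leaves unclear whether the window governs the rating or its entry into the system. PGIC is in any case only summarized descriptively (section 9.4.3.2).

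**Working it through.** The plan states no figure for late ratings, CGIC effect size or CGIC power, so there is nothing of its own to reproduce. The check is calendar arithmetic followed by an illustration on labelled assumptions.

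**Timing**

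- Latest call, counted from a Visit 9 held on Day 99: 99 + 7 = Day 106.
- Part B Day 1 is Part A Day 99, so Day 106 is Part B Day 106 − 99 + 1 = 8.
- Former placebo participant who rolled over (Table 5): 7 days completed at 5 mg/kg/day, with the 10 mg/kg/day step scheduled for Day 8.
- Participant in taper (Table 1): 1 − 7 × 0.10 = 30% of the dose left, or 1 − 8 × 0.10 = 20% if the first cut falls on the Visit 9 day.
- Visit 9 has its own ±7-day window, so the latest call ranges from Day 99 (visit on Day 92) to Day 113 (visit on Day 106). If the questionnaire window is instead read around nominal Day 99, a call can come up to 14 days after a visit held on Day 92.

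**What already protects the rating**

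At the visit, questionnaires precede blood draws, and the first PK sample precedes the morning dose. A rating made at the visit as scheduled therefore comes before the new dosing. That order cannot protect a call made days later.

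**Illustrative size**

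Section 4.2 puts onset of effect at about 1 to 2 weeks and maximum effect at about 1 month. Ratings 0 to 7 days after the visit would mostly precede or just reach onset. The assumed inputs are the share of placebo ratings made late and the share of the full effect reached by then.

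Dilution = share late × share of effect reached.

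Power with late ratings kept = Φ(2.802 × (1 − dilution) − 1.960), where 2.802 = 1.960 + 0.842 corresponds to an assumed 80% power at two-sided 0.05.

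Power with late ratings excluded in both arms = Φ(2.802 × √(1 − share late) − 1.960).

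| Share late | Share of effect | Dilution | Power, kept | Power, excluded | Placebo ratings at 60 per arm |
|---|---|---|---|---|---|
| 2% | 10% | 0.02 × 0.10 = 0.2% | 79.8% | 79.2% | 1.2 |
| 5% | 25% | 0.05 × 0.25 = 1.25% | 79.0% | 78.0% | 3 |
| 10% | 25% | 0.10 × 0.25 = 2.5% | 78.0% | 75.7% | 6 |

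This is a two-arm normal approximation, not the planned hierarchical ordinal model. It covers only placebo ratings after rollover; the taper route is not quantified. In these scenarios exclusion costs more power than retention, so the gain has to come from earlier collection.

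**The case against.** The strongest reply is that the harm is negligible. The rule applies only when the main caregiver is absent, it prefers the day of the visit, and a late rating may be better than none. The first Part B week is at 5 mg/kg/day and mostly precedes the stated onset, so crediting 25% of the full effect to every late placebo rating is generous, as is treating every such participant as having rolled over. Counts at 60 per arm use the maximum sample size, and accrual could stop at 60 randomized, about 30 per arm. All of this stands and limits the point to a minor one.

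A second reply is that a late call may be meant to record the caregiver's view as of Visit 9. The wording allows that reading, and the CGIC item and its recall period are not in the text reviewed. But nothing instructs the caregiver to disregard the days since the visit, so the risk remains.

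A third is that the treatment policy estimand, or a windowing rule in the SAP or Adaptive Design Report (ADR), may cover the matter. The estimand is CGIC at Week 14, and planned rollover to active drug is not named as an intercurrent event. The detailed SAP and ADR are not in the text reviewed and may hold such a rule. It could only flag or drop a late rating; it could not recover one that was not taken in time.

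Finally, a pre-visit window cannot cure an unforeseen absence. That is true, and for those participants the main analysis would be unchanged.

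**Conclusion.** The concern holds, as a minor point. Section 8.2.1 as written permits the single Week 14 CGIC to be taken as late as Part B Day 8, and no provision in the text reviewed ties it to the first Part B or taper dose. The timing follows directly from the documents.

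The size does not. In the assumed scenarios the arm difference shrinks by 0.2% to 2.5%, and an assumed 80% power falls by 0.2 to 2.0 percentage points. The direction is most likely toward no difference. Confidence is medium, because the frequency of late calls is unknown and the detailed analysis documents could not be seen.

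**What to change.** In section 8.2.1, for Part A Visit 9 only:

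- Require the CGIC within −7 to 0 days of the visit and before the first Part B or taper dose, with date and time recorded. This keeps the early half of the window already allowed.
- Rate participants who stopped IMP early but remain in the study as scheduled.
- Flag any rating still made later, keep it in the main analysis, and report one sensitivity analysis without the flagged ratings.
- State whether the physician questionnaire window applies to the rating or to its recording. If it applies to the rating, use the same Visit 9 limit for PGIC.

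Leave ±7 days in place at the other visits.

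The cost is one sentence in section 8.2.1, a date and time check in the questionnaire system, and one sensitivity analysis. The downside is that a few caregivers may not be reachable before the visit; their later ratings would be flagged and retained, so no data are lost relative to the current plan.
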